4.1. Screening, eligibility, recruitment and loss to follow-up of participants

[figure not shown]
CONSORT flow diagrams will be used to summarise the number of participants in each trial arm who were:

- assessed for eligibility at screening ineligible at screening* eligible and randomised received at least one dose of allocated trial intervention received all 28 doses of allocated trial intervention
- seen at 6 months not seen at 6 months censored before 6 months*

The CONSORT flow diagrams will be shown separately for preterm infants and term SGA infants.

Figure 1. CONSORT flowchart

^{*}reasons for these events will be provided.

4.2. Baseline participant characteristics

Demographic and clinical characteristics of the enrolled groups at baseline will be described for each of the analysis populations. This will be done, overall, by trial arm, and by setting. Means and standard deviations will be used to summarise continuous, approximately normally-distributed characteristics; medians and interquartile ranges will be used to summarise continuous, non-normally-distributed characteristics; frequency and proportions will be used to summarise categorical characteristics.

4.3. Protocol adherence and participant follow-up

Protocol deviations are defined as any divergence from the approved study protocol. This includes enrolling ineligible participants, incorrect randomisation procedures, missing required data, and failure to follow approved study procedures. All important protocol deviations, including enrolment errors and procedural violations, will be summarized descriptively. The number and type of deviations will be presented overall and by study arm.

For each analysis population, the number and proportion of participants who receive each treatment dose will be summarised, for doses from days 1 through 28, overall and by trial arm. A summary of the number of doses received will also be calculated, as median and interquartile range, both overall and by study arm.

The number and proportion of participants who are seen at each 4-weekly visit and at the month six visit will also be summarised overall and by study arm. Characteristics of participants who are lost to follow-up will be compared to characteristics of participants who complete the six-month follow-up. Characteristics of participants who are lost to follow-up will be compared between trial arms.

5. Analysis of outcomes

5.1. Primary outcome definitions

- Mortality from enrolment to 6 months of age among preterm infants: the proportion of infants who die from any cause from enrolment to 6 months of age.
- Underweight-free survival from enrolment to 6 months of age among term SGA infants: the proportion of infants with WAZ ≥ -2 at 6 months of age and who have not died.

5.3. Analysis methods

Binary outcomes

The numerator, denominator and proportion with the outcome will be presented overall and by trial arm. A risk ratio comparing the proportion with the outcome in the intervention arm to the proportion

with the outcome in the control arm, along with a 95% confidence interval, will be calculated. As the randomisation is stratified by setting, the analysis will adjust for setting. This will be done using a binomial regression model with a log link function, and including both trial arm and setting as covariates. Binomial regression models can experience model convergence issues under certain circumstances; in this event we will instead use a modified Poisson regression approach with robust standard errors to estimate risk ratios and 95% confidence intervals.

Continuous outcomes

The number of participants, and the mean and standard deviation of the outcome will be presented overall and by trial arm. A difference in means comparing the intervention arm with the control arm, along with a 95% confidence interval will be calculated. As the randomisation is stratified by setting, the analysis will adjust for setting. This will be done using a multiple linear regression model, including trial arm and setting as covariates.

Rate outcomes

The number of episodes and the total person-time of follow-up will be presented overall and by trial arm. An incidence rate ratio comparing the intervention arm with the control arm, along with a 95% confidence interval, will be calculated. This will be done using Poisson regression with a random effects model to allow for multiple episodes occurring in some children, and including trial arm and setting as covariates. If the rate of the outcome varies over the follow-up time, then a Lexis expansion approach will be used to stratify the analysis, and allow the rate to vary by follow-up time period.

Checking assumptions

For statistical analyses of continuous outcomes that require data to be normally distributed, the normality assumption of the data will be checked using graphical assessment of normality (Q-Q plot) and a Kolmogorov-Smirnov test for normality. If the data are found to be non-normal, medians (IQR) or geometric means (GMs) will be presented instead of means (SD). A log transformation will be applied to achieve normality and if not achieved, alternative tests such as the Wilcoxon rank sum test will be used to compare outcomes between trial arms. If normality is achieved through log transformation, then the parametric tests described above will be applied to the log transformed data.

Covariate adjustment

Adjustment for baseline covariates that are prognostic for the outcome has been shown to increase power to detect an intervention effect. For the primary outcomes, we therefore plan to further adjust for birth weight, receiving human milk at the time of randomisation (yes/no), receipt of any antibiotics at the time of randomisation (yes/no) and maternal education (none vs any), factors which have all been shown to be prognostic for the primary outcomes in their respective populations. Adjustment will be done within the binomial regression framework described above (or in the case of convergence issues, Poisson regression with robust standard errors).

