2.3. Sample size

The primary outcome for preterm infants is mortality at 6 months, which is assumed to be 10% in the control arm. A total of 8,602 preterm infants with data on this outcome would be needed for 90% power to detect a 20% relative reduction in mortality risk at 6 months in the intervention arm (i.e. 8% versus 10%), with 5% significance level. The 9,500 preterm infants expected to be enrolled across the 5 sites will allow 9% loss to follow up in determining the primary endpoint among preterm infants for a total of 9,453 preterm infants enrolled.

The primary outcome for term SGA infants is underweight free survival at 6 months, which is assumed to be 23% in the control arm. A total of 3,750 term SGA infants with data on this outcome would be needed for 90% power to detect a 20% relative improvement in underweight free survival in the intervention arm (i.e. 27.6% versus 23%), at 5% significance level. The 4,500 term SGA infants expected to be enrolled across the 5 sites will allow 16% loss to follow up in determining the primary endpoint among term SGA infants for a total of 4,465 term SGA infants enrolled.

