5.6. Subgroup analyses

We will assess whether the effect of probiotic supplementation on the primary outcomes differs in the following subgroups, listed according to whether the subgroups are defined pre-randomisation or post-randomisation.

Pre-randomisation:

- prematurity (2 groups): <32weeks, 32-<37 weeks, among preterm infants only
- birth weight (3 groups): < 1.5kg, 1.5 to < 2.5kg, 2.5+ kg
- preterm and SGA status (2 groups): preterm SGA, preterm AGA among preterm infants only
- early initiation of enteral feeding (including mother's milk, donor milk, infant formula) (3 groups): within < 1hour, 2-< 24hour, 24+ hours after birth

Post-randomisation:

- vaccination according to vaccine schedule from enrolment to 6 months (3 groups): fully vaccinated, partially vaccinated, not vaccinated
- feeding type at 1 month of age (3 groups): exclusive, predominant, partial
- feeding type at 3 months of age (3 groups): exclusive, predominant, partial
- feeding type at 6 months of age (3 groups): exclusive, predominant, partial
- any micronutrient supplement intake from enrolment to 6 months of age (2 groups): any, none
- iron supplement intake from enrolment to 6 months of age (2 groups): any, none
- vitamin A supplement intake from enrolment to 6 months of age (2 groups): any, none
- vitamin D supplement intake from enrolment to 6 months of age (2 groups): any, none
- zinc supplement intake from enrolment to 6 months of age (2 groups): any, none
- receipt of antibiotics from enrolment to 6 months of age (2 groups): yes, no

For subgroups defined pre-randomisation, this will be done by summarising results separately for each sub-group, and fitting a regression model including an interaction term between trial arm and subgroup indicator, and presenting the effect of the intervention within each subgroup. Interaction terms will be assessed for strength of evidence against the null hypothesis of no effect modification, using likelihood ratio tests.

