5.7. Statistical software

All analysis will be conducted in Stata and R.

5.8. Sample tables for baseline characteristics, primary outcomes and selected secondary outcomes

Table 1: Baseline characteristics of **preterm infants** by trial arm, primary ITT analysis population

	Co	Control arm		
Characteristic	n	n Col%		Col%

Table 2: Baseline characteristics of term SGA infants by trial arm, primary ITT analysis population

	Control arm		Intervention arm	
Characteristic	n	Col%	n	Col%

Table 3: The effect of probiotic supplementation on primary outcomes in preterm children and in term SGA children, primary ITT analysis populations

	Placebo	Intervention		
Population; outcome	n/N (%)	n/N (%)	Risk ratio (95% CI)	P value
Preterm children; All-cause mortality, enrolment to 6 months				
Term SGA children; Underweight-free survival, enrolment to 6 months				

Table 4: The effect of probiotic supplementation on secondary outcomes (all cause and cause specific mortality) among **preterm children**, primary ITT analysis populations

	Placebo	Intervention		
Outcome	n/N (%)	n/N (%)	Risk ratio (95% CI)	P value
All cause mortality at hospital discharge				
All cause mortality at 1 month				
Mortality due to necrotising enterocolitis at hospital discharge				
Mortality due to necrotising enterocolitis at 1 month				
Mortality due to necrotising enterocolitis at 6 months				
Mortality due to sepsis at hospital discharge				
Mortality due to sepsis at 1 month				
Mortality due to sepsis at 6 months				
Mortality due to severe diarrhoea at hospital discharge				
Mortality due to severe diarrhoea at 1 month				
Mortality due to severe diarrhoea at 6 months				

Table 5: The effect of probiotic supplementation on secondary outcomes (all cause and cause specific mortality) among **term SGA children**, primary ITT analysis populations

	Placebo	Intervention		
Outcome	n/N (%)	n/N (%)	Risk ratio (95% CI)	P value
All cause mortality at hospital discharge				
All cause mortality at 1 month				
All cause mortality at 6 months				
Mortality due to necrotising enterocolitis at hospital discharge				
Mortality due to necrotising enterocolitis at 1 month				
Mortality due to necrotising enterocolitis at 6 months				
Mortality due to sepsis at hospital discharge				
Mortality due to sepsis at 1 month				
Mortality due to sepsis at 6 months				

Mortality due to severe diarrhoea at hospital discharge		
Mortality due to severe diarrhoea at 1 month		

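### Covariate adjustment omits gestational age for preterm mortality and stops at the primary outcomes, so mean WAZ and WLZ lose precision that baseline data could supply

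*SAP*

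**What the plan says.** Section 5.3, under covariate adjustment, gives power as the reason for adjusting. For the primary outcomes only, it says "we therefore plan to further adjust for birth weight, receiving human milk at the time of randomisation (yes/no), receipt of any antibiotics" at randomisation, and closes the list with maternal education. These covariates are added within the same binomial regression framework, with modified Poisson regression as the fallback if the model does not converge.

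Gestational age is not listed. Yet section 5.6 places it among the subgroups defined before randomisation: "prematurity (2 groups): <32weeks, 32-<37 weeks, among preterm infants only". Section 2.2 stratifies randomisation by site and by preterm or term SGA status, so gestational age within the preterm group is not balanced by design.

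For continuous outcomes, which include mean WAZ and mean WLZ at 6 months, section 5.3 states: "This will be done using a multiple linear regression model, including trial arm and setting as covariates". No baseline covariate is added for them.

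The term SGA primary outcome, underweight-free survival, contains a WAZ threshold (section 5.1) and, as a primary outcome, is adjusted for birth weight.

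**The concern.** The SAP sets its own criterion, prognostic value at baseline, and then does not apply it in two places where it would be expected to matter.

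- **Preterm mortality.** Gestational age is a natural prognostic candidate for death in preterm infants. Birth weight is only a partial substitute: section 5.6 itself separates preterm SGA from preterm AGA infants, which recognises that infants of similar weight can differ in maturity.
- **Mean WAZ and WLZ at 6 months.** Size at birth is an obvious candidate predictor of size at 6 months. Birth weight is already used in the primary models but is left out here.

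At stake is the width of confidence intervals. The bias, type I error and stated power of the planned analyses are not in question.

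**Working it through.** **1. The plan's own figures (section 2.3).** The inputs for preterm infants are a 6-month risk of death of 10% on control against 8% on intervention, 90% power and a 5% level. Tests are two-sided (section 3.1) and allocation is 1:1 (section 2.2). The stated result is: "A total of 8,602 preterm infants with data on this outcome would be needed for 90% power to detect a 20% relative reduction".

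Pooled two-proportion formula, per arm: n = [1.960·√(2p̄(1−p̄)) + 1.2816·√(p₁(1−p₁)+p₂(1−p₂))]² / (p₁−p₂)².

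- Preterm: p̄ = 0.09, so [1.960·√0.1638 + 1.2816·√0.1636]² / 0.02² = (0.7932 + 0.5184)² / 0.0004 = 4,300.7. This rounds up to 4,301 per arm, or 8,602 in total, as stated. For loss to follow-up, 8,602 / 0.91 = 9,453, matching "will allow 9% loss to follow up in determining the primary endpoint among preterm infants for a total of 9,453 preterm infants enrolled".
- Term SGA, 23% versus 27.6%: 1,875 per arm, or 3,750 in total, as stated. Then 3,750 / 0.84 = 4,465, as stated.

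Neither calculation uses a covariate. Leaving one out therefore cannot make the stated 90% power wrong.

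**2. Mean WAZ and WLZ with birth weight added.** The SAP gives no correlation r between birth weight and the 6-month score. The range 0.2 to 0.5 is an assumption. Adjustment multiplies the variance of the mean difference by 1 − r², and the equivalent gain in infants is 1/(1 − r²) − 1.

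| r | Variance reduction | SE ratio | Equivalent extra infants |
|---|---|---|---|
| 0.2 | 4% | 0.980 | 4.2% |
| 0.3 | 9% | 0.954 | 9.9% |
| 0.4 | 16% | 0.917 | 19.0% |
| 0.5 | 25% | 0.866 | 33.3% |

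Example with an assumed SD of 1.0 and 3,750 infants: the 95% CI half-width is 1.96 × √(4/3,750) = 0.064. It becomes 0.061 at r = 0.3 and 0.055 at r = 0.5. The 3,750 includes infants who die and so have no 6-month score, so all three widths are slightly optimistic; their ratios are unaffected.

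**3. Preterm mortality with gestational age added to birth weight.** The SAP gives no prognostic strengths, so a range was assumed and simulated: 8,602 infants, 10% control risk, risk ratio 0.80, modified Poisson with robust SE, 300 replicates per scenario. Power is Φ(|ln 0.80|/SE − 1.96), using the mean SE. Rejection rates counted over 300 replicates are too noisy to compare the models: their Monte Carlo SE is about √(0.9 × 0.1/300) = 1.7 points. OR is per SD decrease; GA is gestational age and BW is birth weight.

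| OR, GA | OR, BW | Correlation | SE: none / BW / BW+GA | Power: none / BW / BW+GA |
|---|---|---|---|---|
| 1.3 | 1.8 | 0.7 | 0.0691 / 0.0674 / 0.0673 | 0.898 / 0.912 / 0.912 |
| 1.5 | 1.5 | 0.7 | 0.0692 / 0.0679 / 0.0676 | 0.897 / 0.908 / 0.910 |
| 2.0 | 1.5 | 0.7 | 0.0692 / 0.0671 / 0.0664 | 0.897 / 0.914 / 0.920 |
| 2.0 | 1.5 | 0.5 | 0.0691 / 0.0676 / 0.0665 | 0.898 / 0.910 / 0.918 |
| 2.5 | 1.5 | 0.5 | 0.0690 / 0.0672 / 0.0655 | 0.899 / 0.913 / 0.926 |

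Gestational age adds between 0 and 1.3 power points beyond birth weight. In effective sample size the range runs from (0.0674/0.0673)² = 1.003 to (0.0672/0.0655)² = 1.053. Setting and the other three covariates were left out of the simulation.

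**The case against.** The strongest reply is that nothing here is wrong. A short covariate list is pre-specified, randomisation protects validity whichever covariates are chosen, and no stated figure changes. All of that stands, and it sets the weight of the point.

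Further objections also have force:

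- **The gain for preterm mortality is small.** Birth weight already carries much of the information in gestational age, and the outcome is binary at 8% to 10%. A reader might infer that hundreds of infants' worth of information is being discarded. The SAP gives no prognostic strength that would support such a figure, and the simulated gain includes values near zero.
- **The growth gain depends on an unknown correlation.** Term SGA infants are selected for small size. This narrows the birth-weight range and would tend to pull the correlation towards the lower end.
- **Growth is not wholly unadjusted.** A reader might infer that no growth outcome is adjusted for birth weight. That is not so: underweight-free survival is.
- **More covariates can cost stability.** Section 5.3 warns that log-binomial models may fail to converge. Where events may be few, as with the cause-specific deaths in Tables 4 and 5, extra covariates could do harm.

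A reader might also infer two rival primary models. Section 5.3 gives a setting-only model and then a further-adjusted one, Table 3 in section 5.8 ("The effect of probiotic supplementation on primary outcomes in preterm children and in term SGA children") has one risk ratio per population, and the interim rule in section 2.4 refers back to section 5.3. The natural reading, however, is a single primary-outcome model with arm, setting and the four covariates. That reading fits Table 3 and section 2.4. An explicit sentence would help, but the text does not show a real choice between two tests.

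**Conclusion.** The point holds as a nearly costless gain in precision. The omission of gestational age from the preterm mortality model, and of any baseline covariate from the models for mean WAZ and WLZ, sits awkwardly with the SAP's own reason for adjusting.

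The larger benefit is likely in mean WAZ and WLZ: 4% to 25% less variance if the correlation with birth weight is 0.2 to 0.5. For preterm mortality the benefit is about 0 to 1.3 power points, if the odds ratios per SD are 1.3 to 2.5 for gestational age and 1.5 to 1.8 for birth weight, with a correlation of 0.5 to 0.7. None of these strengths comes from the SAP.

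A reader might go further and infer that the trial is underpowered or that its sample sizes need revision. The documents do not support this: 8,602 and 3,750 follow from unadjusted formulas, and both reach 90% power as stated.

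**What to change.** In section 5.3:

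1. Add birth weight to the linear models for mean WAZ and mean WLZ in both populations, and continuous gestational age as well in preterm infants.
2. Add continuous gestational age to the adjusted preterm mortality model, keeping the modified Poisson fallback already specified.
3. Do not extend the adjustment to the sparse cause-specific secondary outcomes.
4. Optionally, add one sentence saying that the covariate-adjusted model supplies the Table 3 risk ratio and P value and the interim p-value.

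The cost is SAP wording. Both variables are known before randomisation; the one assumption is that gestational age is recorded in weeks or days and not only in the two bands of section 5.6. The change should be made before anyone choosing the model sees results by arm, so that the choice cannot be data-driven.

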5.5. Missing data

The primary analysis approach will be based on complete case analysis. However, for any outcome where >10% outcome data are missing, multiple imputation methods will be used, assuming that data are missing at random. Results from MI analyses will be presented alongside results from complete case analysis.

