3.1. Confidence intervals and p-values

All applicable statistical tests will be two-sided and 95% confidence intervals will be presented.

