3.3. Analysis populations

The primary analysis populations will be:

- All randomised preterm infants (Preterm ITT)
- All randomised term SGA infants (Term SGA ITT)

For primary outcome 1 (mortality in preterm infants), all randomised preterm infants will be the analysis population.

For primary outcome 2 (underweight free survival in term SGA infants), all randomised term SGA infants will be the analysis population.

For all secondary outcomes, analyses will be conducted and presented separately for the two analysis populations.

The primary analysis will be done by intention to treat (ITT), i.e. participants will be included according to the trial arm they were randomised to, regardless of whether interventions were received. The only exception to this will be if the participant's mother withdraws their consent for their data to be used.

Missing data will be handled using complete case analysis as the primary approach. Multiple imputation methods may also be used as a sensitivity analysis if substantial missing data exist (>10% missing).

"Per-protocol" secondary analyses will also be conducted, among the following populations, with participants analysed according to the treatment received rather than the treatment to which they were randomised (if the two differ):

- Randomised preterm infants who receive all 28 days of intervention/control (Preterm PP): for primary outcome 1 and all secondary outcomes
- Randomised term SGA infants who receive all 28 days of intervention/control (Term SGA PP): for primary outcome 2 and all secondary outcomes

4. Trial population

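### Complete-case analysis of preterm 6-month mortality drops infants lost alive and so inflates the reported risks; at the planned 9% loss no missing-data analysis is triggered, although the risk ratio is affected only if loss differs by arm

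*SAP*

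**What the plan says.** Section 5.1 defines the preterm primary outcome as a simple proportion dying between enrolment and 6 months. Section 2.6 takes deaths from active and passive SAE reporting. Section 5.3 analyses the outcome with a log-binomial model (modified Poisson as fallback) that makes no use of follow-up time.

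On missing outcomes, section 3.3 says "Missing data will be handled using complete case analysis as the primary approach" and then "Multiple imputation methods may also be used as a sensitivity analysis if substantial missing data exist". Section 5.5 keeps complete case as primary but is firmer on imputation: "for any outcome where >10% outcome data are missing, multiple imputation methods will be used". One section therefore says *may* and the other *will*. Both set the threshold at more than 10% missing.

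Section 2.3 states that "A total of 8,602 preterm infants with data on this outcome would be needed for 90% power" and that the expected enrolment "will allow 9% loss to follow up in determining the primary endpoint among preterm infants". An infant lost to follow-up is thus treated as having no primary endpoint. For term SGA infants the corresponding allowance is 16%.

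**The concern.** A death completes the outcome on the day it is reported. An infant last seen alive at month 5 has no 6-month status and is dropped, although five months of survival are known. Whether an infant is a complete case therefore depends partly on the outcome. The denominator loses survivors more readily than deaths, and the estimated risk is too high even when loss is unrelated to prognosis.

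The stated safeguard is imputation, and it starts only above 10% missing. If preterm loss runs to plan, the mortality outcome gets no missing-data analysis. The stakes are the absolute mortality risks in both arms and, if retention differs by arm, the risk ratio and its type I error.

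**Working it through.** **1. The plan's own figures.** Inputs: control risk 10% ("mortality at 6 months, which is assumed to be 10% in the control arm"), intervention risk 8%, 1:1 allocation (section 2.2), 90% power, "with 5% significance level", and two-sided tests (section 3.1: "All applicable statistical tests will be two-sided"). With pooled variance under the null:

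n per arm = [1.960·√(2·0.09·0.91) + 1.282·√(0.10·0.90 + 0.08·0.92)]² / 0.02² = 4,300.7, so 4,301 per arm and 8,602 in total.

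8,602 / (1 − 0.09) = 9,453. Both stated figures reproduce exactly.

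**2. Planned loss against the trigger.** At 9,453 enrolled, loss is 9%. At the expected 9,500 it is 1 − 8,602/9,500 = 9.45%. Both are below the 10% threshold, by 1.0 and 0.55 points. Term SGA at 16% is above it.

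**3. Complete-case risk under random loss.** Let p be the true 6-month risk and L the probability of a loss time before 6 months, independent of death. Let s be the share of deaths that come before loss among infants with both.

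- Known deaths: p(1 − L) + pLs
- Known survivors: (1 − p)(1 − L)
- Missing: m = L(1 − ps)
- Complete-case risk: p[1 − L(1 − s)] / (1 − m)

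The SAP gives no timing. Assume 70% of deaths and 30% of losses fall in the first 28 days, uniformly within each period. Then s = 0.7·0.7 + ½·0.7·0.3 + ½·0.3·0.7 = 0.70.

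**4. Equal loss, m = 9% in both arms.**

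- Control: L = 0.09/0.93 = 0.0968; risk = 0.10 × 0.9710/0.91 = 10.7%
- Intervention: L = 0.09/0.944 = 0.0953; risk = 0.08 × 0.9714/0.91 = 8.5%
- Risk ratio = 0.800

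Other timing assumptions, with 9% missing on average over the two arms:

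| s | Control | Intervention | Risk ratio |
|---|---|---|---|
| 0.5 | 10.5% | 8.4% | 0.801 |
| 0.8 | 10.8% | 8.6% | 0.801 |
| 1.0 | 11.0% | 8.8% | 0.802 |

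A Kaplan-Meier risk under the same random loss returns 10% and 8%.

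**5. Unequal loss, no true effect (10% in both arms), s = 0.70.** The standard error of the log risk ratio is about √(2·0.9/430) = 0.065. Type I error = 1 − Φ(1.96 − δ) + Φ(−1.96 − δ), where δ = ln(RR)/SE.

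| Missing, intervention vs control | Risks | RR | Type I error |
|---|---|---|---|
| 7.4% vs 9.3% (L = 8% vs 10%) | 10.54% vs 10.69% | 0.986 | about 5.5% |
| 6.6% vs 11.6% | 10.48% vs 10.89% | 0.962 | about 9% |

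The standard error at these exact denominators is 0.062, which gives 5.6% and 9.4%. Average missingness is 8.4% and 9.1%, so imputation is not triggered in either case. If the intervention arm loses more, the bias reverses. If the true risk ratio is 0.80, the 5-point gap gives 8.39%/10.89% = 0.77.

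**6. Tipping point at the design result.** Take 344 vs 430 deaths of 4,301 (z = 3.24, p = 0.001), about 425 lost per arm, and lost controls dying at 10%. Significance is lost when lost intervention infants die at about 17.1% (z = 1.97 at 17.1%, 1.95 at 17.2%).

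**The case against.** Several stronger readings are tempting, and the SAP does not support them.

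- *Random loss biases the trial's result.* It biases the absolute risks. The planned effect measure is the risk ratio, which with equal loss moves from 0.800 to at most 0.802.
- *Nothing in the plan would reveal differential loss.* Section 4.1 reports infants not seen or censored before 6 months by arm, with reasons for censoring. Section 4.3 tabulates attendance by arm and compares the lost infants between arms. Detection is planned; what is missing is any measure of the effect on the estimate.
- *Type I error is doubled.* That needs a gap of about five points. The trial is double-blind with identical sachets (section 2.2), and the document gives no reason to expect such a gap. At two points the error is about 5.5%.
- *Complete case contradicts the population of all randomised preterm infants.* Section 3.3 defines a set by allocation and then a rule for missing outcomes within it. That is an ordinary ITT set with a missing-data rule.
- *The loss is large against the effect.* The 851 planned losses (9,453 − 8,602) against 86 fewer deaths (430 − 344) compares infants with deaths and does not measure bias. The tipping point suggests reasonable robustness: lost intervention infants would have to die at more than 1.7 times the rate of lost controls.

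It can also be said that the premise is inferred. The SAP never says how an infant last seen alive is classed, SAE reporting includes a passive channel, and 9% is an allowance rather than a forecast. This stands as a limit on size: vital status may be known for more than 91%. It does not remove the point. Treating every infant without a reported death as alive would leave no loss in determining the endpoint, which conflicts with section 2.3.

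**Conclusion.** The point holds in limited form. If loss runs to plan, the preterm primary outcome is reported with mortality risks about half to one percentage point too high in the control arm and slightly less in the intervention arm. No missing-data analysis accompanies them. The risk ratio is essentially right unless retention differs by arm. With no true effect it is then off by about 1% for a 2-point gap and about 4% for a 5-point gap.

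These sizes rest on loss that is independent of death within each arm, on the assumed timing of deaths and losses, and on the inferred classification of infants lost alive. The gap below the trigger and the *may*/*will* mismatch rest on the text alone. The trigger problem concerns preterm mortality only, since the term SGA allowance already exceeds 10%. This is worth correcting, but it does not show that the planned primary model is invalid.

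**What to change.** 1. Keep the setting-adjusted log-binomial risk ratio as the primary analysis. Replacing it with a time-to-event method is a debatable trade-off that these figures do not compel.
2. State how an infant last known alive before 6 months is classed.
3. For preterm mortality, always report beside the primary result a site-adjusted 6-month risk per arm and risk ratio from time to death, censored at last contact known alive, using Kaplan-Meier risks or inverse-probability-of-censoring weights.
4. Always add a tipping-point analysis for preterm mortality, varying the death risk among lost infants separately by arm.
5. Remove the 10% trigger for the primary outcomes. Any imputation of mortality should condition on survival to last contact. Imputing from baseline covariates alone would give lost infants roughly the inflated complete-case risk.
6. Use the same wording on imputation in sections 3.3 and 5.5.

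The cost is SAP wording, a few extra programs and slightly more reporting. The 4-weekly visits in section 2.6 should supply last-contact dates. It is best settled before the interim efficacy analysis, which uses the section 5.3 methods.
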